6.5.2 Prohibited Concomitant Therapy

A subject cannot participate in another clinical trial for the treatment of COVID-19 until after Day 29 (see exclusion criteria).

Once enrolled, concomitant medications for the treatment of COVID-19 as described in written policy or guideline (i.e., not just an individual clinician decision) are permitted. In the absence of a local written standard of care, the National Institutes of Health (NIH) COVID-19 Treatment Guidelines may be used (<https://www.covid19treatmentguidelines.nih.gov/>). This includes anti-inflammatory medications such as dexamethasone and convalescent plasma. Concomitant use of any other experimental treatment or off-label use of marketed medications intended as specific treatment for COVID-19 or SARS-CoV-2 infection, and not specified in the local or NIH COVID-19 Treatment Guidelines are prohibited. Specifically, use of any biologic therapy not specified on the written policy or guideline are prohibited including: monoclonal antibodies targeting cytokines (e.g., TNF inhibitors; interleukin-1[IL-1], IL-6 [tocilizumab or sarilumab]), or T-cells (e.g., abatacept); monoclonal antibodies targeting B-cells (e.g., rituximab, and including any targeting multiple cell lines including B-cells); JAK inhibitor(s) (e.g., baricitinib, imatinib, gefitinib, acalabrutinib); and any type of interferon, convalescent plasma, or immunoglobulin (IgG) therapies for COVID-19. Similarly, the concomitant use of hydroxychloroquine to treat COVID-19 is prohibited unless it is included in the local institutional treatment guidelines.

On August 23, 2020, the FDA issued an EUA for COVID-19 convalescent plasma for the treatment of hospitalized patients with COVID-19. The NIH COVID-19 Treatment Guidelines were updated on September 1, 2020 and concludes that “there are insufficient data to recommend either for or against the use of convalescent plasma for the treatment of COVID-19”. According to the NIH Guidelines and the EUA Fact Sheet for Health Care Providers, convalescent plasma should not be considered the standard of care for the treatment of patients with COVID-19. However, if a site has adopted convalescent plasma as part of their institutional standard of care for the treatment of COVID-19 patients, it is allowed as described above.

Concomitant medications will be assessed from 7 days prior to enrollment to Day 29 or upon discharge, whichever comes first. All prescription medications should be recorded during this

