Appendix D - ACTT-4: Baricitinib/Remdesivir vs Dexamethasone/Remdesivir

CI 1.4 to 3.6). Baricitinib also showed benefit to those on low flow oxygen with a median of 5 days to recovery compared with 6 days in control group (RRR 1.17, 95% CI 0.98 to 1.39) and the clinical improvement by day 15 (OR 1.2; 95% CI 0.9 to 1.6). Patients who received combination treatment with baricitinib and remdesivir and those in the control arm had a similar incidence of adverse and serious adverse events including infections and venous thromboembolic events (VTE). On November 19, 2020, the FDA issued an Emergency Use Authorization (EUA) for the use of baricitinib in combination with remdesivir in hospitalized adults and children aged ≥ 2 years with COVID-19 who require supplemental oxygen, invasive mechanical ventilation, or extracorporeal membrane oxygenation (ECMO).

The Randomized Evaluation of Covid-19 Therapy (RECOVERY) trial is a controlled, open-label randomized trial, involving all major hospitals in the UK. The trial compared a range of possible treatments in patients who were hospitalized with Covid-19. Included, was a treatment arm assigned to receive oral or intravenous dexamethasone (at a dose of 6 mg once daily for up to 10 days) or to received usual care alone. Overall, 22.9% in the dexamethasone group and 25.7% in the usual care group died within 28 days after randomization (age-adjusted rate ratio, 0.83; 95% confidence interval [CI], 0.75 to 0.93; $P < 0.001$). In the dexamethasone group, the incidence of death was lower than that in the usual care group among patients receiving invasive mechanical ventilation (29.3% vs. 41.4%; rate ratio, 0.64; 95% CI, 0.51 to 0.81) and among those receiving supplemental oxygen without invasive mechanical ventilation (23.3% vs. 26.2%; rate ratio, 0.82; 95% CI, 0.72 to 0.94) but not among those who were receiving no supplemental oxygen respiratory support at randomization (17.8% vs. 14.0%; rate ratio, 1.19; 95% CI, 0.91 to 1.55). Remdesivir was not used routinely in the RECOVERY trial.

The ACTT-2 and RECOVERY trials are very different:

- ACTT 2 randomized patients to baricitinib, a JAK inhibitor and RDV or RDV alone. RECOVERY randomized patients to dexamethasone or standard care.
- Different study populations – ACTT-2 had more restrictive study criteria due to the use of remdesivir and baricitinib. Exclusions for liver or renal dysfunctions or cytopenias may have selected for a less ill population compared to RECOVERY.

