4.2 Scientific Rationale for Study Design

This study utilizes an adaptive platform design that increases efficiency to identify safe and efficacious therapeutic agents for patients with COVID-19 during the current outbreak. In addition, the adaptive design allows for the evaluation of new therapeutic agents as they are identified and ready for testing in clinical trials. As the study is a multicenter, multinational randomized controlled study, we will be able to acquire rigorous data about the safety and efficacy of investigational therapeutic agents for COVID-19 that will lead to generalizable evidence. Randomization is essential for establishing efficacy of these new therapeutic agents. Last, collecting clinical and virologic data on enrolled subjects using a standardized timeline and collection instruments should provide valuable information about the clinical course of and morbidities associated with COVID-19 in a diverse group of hospitalized adults with confirmed SARS-CoV-2 infection.

The ACTT-4 design will specifically evaluate the contributions of blocking inflammatory pathways with the JAK inhibitor baricitinib compared with less specific, anti-inflammatory effects of dexamethasone while all subjects receive the antiviral remdesivir.

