6.5.2 Prohibited Concomitant Therapy

As the study is comparing baricitinib to dexamethasone, additional baricitinib, dexamethasone and other glucocorticoids are prohibited unless the subject worsens and requires invasive mechanical ventilation (see Section 6.5.4). In addition, if oral study product is held for more than two days and the clinical condition requires, an open-label (off-study) dexamethasone or other anti-inflammatory agent may be added while the oral study product is held (Section 6.1.4). Exceptions to the steroid prohibition include: mineralocorticoids for standard indications are permitted (e.g., adrenal insufficiency, shock) and low-dose prednisone as part of immunosuppression regimen for solid organ-transplant patients is allowed (e.g., prednisone 5 mg po daily).

Strong inhibitors of organic anion transporter 3 (OAT3) such as probenecid are prohibited during the study.

Concomitant use of any other experimental treatment or off-label use of marketed medications intended as specific treatment for COVID-19 or SARS-CoV-2 infection, and not specified in the local or NIH COVID-19 Treatment Guidelines are prohibited. Specifically, use of any biologic therapy not specified on the written policy or guideline are prohibited including: monoclonal antibodies targeting cytokines (e.g., TNF inhibitors; interleukin-1[IL-1], IL-6 [tocilizumab or sarilumab]), or T-cells (e.g., abatacept); monoclonal antibodies targeting B-cells (e.g., rituximab, and including any targeting multiple cell lines including B-cells); JAK inhibitor(s) (e.g., baricitinib, imatinib, gefitinib, acalabrutinib, tofasitinib); and any type of interferon, convalescent plasma, or immunoglobulin (IgG) therapies for COVID-19. Similarly, the concomitant use of hydroxychloroquine to treat COVID-19 is prohibited unless it is included in the local institutional treatment guidelines (and even then, it is discouraged given the interaction with remdesivir).

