In ACTT-4, non-study product (off-study) baricitinib, dexamethasone and other glucocorticoids are prohibited unless the subject worsens to require invasive mechanical ventilation (ordinal score 7). Mineralocorticoids for standard indications are permitted (e.g., adrenal insufficiency, shock). Low-dose prednisone as part of immunosuppression regimen for solid organ-transplant patients is allowed as part of standard of care (e.g., prednisone 5 mg po daily).

If additional (off-study) baricitinib, dexamethasone or another glucocorticoid is given when a subject is not an ordinal scale category 7, the investigator should file a protocol deviation for use of the prohibited medication and decide whether the blinded study products should be discontinued. The subject should remain on study and continue with the SOA as described in the protocol though the Day 60 visit. An exception to this is when oral study product is held for more than 2 days and the clinical condition requires that an open-label (off-study) dexamethasone or other anti-inflammatory agent be added while the oral study product is held (see Section 6.1.4).

- The preference is to continue study medication as originally assigned (i.e. continue blinded baricitinib or placebo and continue blinded dexamethasone or placebo) as well as the remdesivir infusions. The subject should remain on study though the Day 60 visit.
- Recognizing the treating clinician may request to stop the randomized blinded study medication, the next preferred option is that the baricitinib/placebo po component and the dexamethasone/placebo IV component are discontinued without unblinding. This will allow the treating clinician to pick any regimen needed for the subject. In this scenario, remdesivir infusions should continue and the subject should remain on study though the Day 60 visit.
- If the treating clinician needs to know prior treatment, the site investigator can request that the subject treatment assignment be unblinded. This is the least preferred option as it unblinds treatment assignment. However, it is available to ensure clinicians have information available to give their patients optimal care. In this scenario, remdesivir infusions should continue and the subject should remain on study through the Day 60 visit.

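### Before category 7, ACTT-4 bans off-study baricitinib and all glucocorticoids outright, but a guideline-listed second JAK inhibitor is not prohibited in either blinded arm

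*Protocol*

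**What the plan says.** All references are to Appendix D (ACTT-4) unless stated.

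- **6.5.2, first paragraph.** Giving as its reason that the trial compares baricitinib with dexamethasone, it says that "additional baricitinib, dexamethasone and other glucocorticoids are prohibited unless the subject worsens and requires invasive mechanical ventilation". The exceptions are an oral-product hold of more than two days, when open-label dexamethasone or another anti-inflammatory drug may be added; mineralocorticoids for standard indications; and low-dose prednisone in solid organ transplant.
- **6.5.4, ban sentence.** It repeats the same scope: off-study "baricitinib, dexamethasone and other glucocorticoids are prohibited unless the subject worsens to require invasive mechanical ventilation".
- **6.5.4, deviation sentence.** The duty to file a deviation and to decide whether to stop the blinded products begins: "If additional (off-study) baricitinib, dexamethasone or another glucocorticoid is given when a subject is not an ordinal scale category 7".
- **6.5.1.** Outpatient COVID-19 drugs backed by a written local guideline may continue, except dexamethasone and baricitinib.
- **6.5.2, third paragraph.** Other COVID-19 treatments are prohibited when no local or NIH guideline specifies them. It then says that "use of any biologic therapy not specified on the written policy or guideline are prohibited including", and the list that follows contains "JAK inhibitor(s) (e.g., baricitinib, imatinib, gefitinib, acalabrutinib, tofasitinib".
- **4.2.** The stage is to "specifically evaluate the contributions of blocking inflammatory pathways with the JAK inhibitor baricitinib compared with less specific, anti-inflammatory effects of dexamethasone".

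**The concern.** The first paragraph of 6.5.2 protects the randomized contrast. On the steroid side it does so for the whole class; on the JAK side it stops at one drug. Every other JAK inhibitor falls to the third paragraph, where a guideline listing lifts the prohibition.

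Two things are at stake. In the dexamethasone arm, an added JAK inhibitor brings in the mechanism that the other arm is meant to represent. In the baricitinib arm, it puts a second JAK inhibitor on top of blinded baricitinib, whose US label (2.2.3.1) carries a boxed warning that includes serious infections and thrombosis. In neither case does 6.5.4 ask for a deviation report or a decision on the blinded products.

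A second, smaller matter is that the third paragraph names baricitinib itself under the guideline condition, two paragraphs after banning it without one. Baricitinib is a drug that a local guideline could well list: 2.1.1 records that on November 19, 2020 "the FDA issued an Emergency Use Authorization (EUA) for the use of baricitinib in combination with remdesivir in hospitalized adults".

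**Working it through.** **Step 1. The rules before category 7, side by side.**

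| Place | Steroid side | JAK side | Lifted by a guideline listing? |
|---|---|---|---|
| 6.5.1 carve-out | dexamethasone | baricitinib only | no |
| 6.5.2, first paragraph | dexamethasone and other glucocorticoids | baricitinib only | no |
| 6.5.4, ban sentence | dexamethasone and other glucocorticoids | baricitinib only | no |
| 6.5.4, deviation sentence | dexamethasone or another glucocorticoid | baricitinib only | not stated |
| 6.5.2, third paragraph | not listed | JAK inhibitors as an entry, baricitinib first | yes |

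Four places name only baricitinib on the JAK side. Three of those four widen the steroid side to the class.

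**Step 2. Follow four cases through the text.**

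1. *Second JAK inhibitor for COVID-19, in no guideline.* Prohibited by the third paragraph of 6.5.2, and a deviation under main protocol 10.1.9.
2. *Second JAK inhibitor for COVID-19, listed in a local or NIH guideline, started after enrollment in category 5 or 6.* The first paragraph does not name it, the third paragraph's condition is not met, and the 6.5.4 deviation sentence does not name it. It is not prohibited.
3. *The same drug taken before entry.* Exclusion 12 bars other small molecule tyrosine kinase inhibitors given for COVID-19 in the two weeks before screening, with no guideline exception. The gap therefore concerns mainly new starts after enrollment.
4. *Off-study baricitinib, guideline-listed.* Banned by the first paragraph and by 6.5.4, and excepted from the guideline allowance in 6.5.1. Only the third paragraph, read alone, suggests a condition.

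**Step 3. Where the list comes from.** The ACTT-3 counterpart (Appendix C, 6.5.2) reads "JAK inhibitor(s) (e.g., baricitinib, imatinib, gefitinib, acalabrutinib); and any type of interferon". That is four drugs. The ACTT-4 entry has five: the same four plus tofasitinib. So 4 of 5 are carried over from a stage in which baricitinib was not a study drug. One of the five, baricitinib, now carries two rules.

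**Step 4. Timing.** From the baricitinib authorization (November 19, 2020) to protocol version 10.0 (January 15, 2021) is 11 + 31 + 15 = 57 days.

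**Step 5. Can the effect be sized?** The plan's own figure first. For 0.85 against 0.90 at two-sided 5% and 80% power, the normal-approximation formula gives 686 per arm, 1372 in total, against the 1382 stated in 9.2 from an exact test. With n = 691 per arm,

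power = Φ{[Δ√n − 1.960√(2p̄q̄)] / √(p₁q₁ + p₂q₂)} = Φ{[0.05 × 26.287 − 1.960 × 0.4677] / 0.4664} = Φ(0.853) = 80.3%,

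against 80% stated. The figure is reproduced.

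Suppose, purely as an assumption, that a fraction f of the dexamethasone arm takes a second JAK inhibitor and gains the full 5 points, so that its proportion becomes 0.85 + 0.05f:

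| f | Dexamethasone arm | Power at N = 1382 |
|---|---|---|
| 0 | 0.850 | 80.3% |
| 2% | 0.851 | 78.8% |
| 5% | 0.8525 | 76.5% |
| 10% | 0.855 | 72.3% |
| 20% | 0.860 | 62.9% |

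The protocol gives no value for f, nor any effect for another JAK inhibitor. The table shows sensitivity only and is not an estimate.

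**The case against.** The case for leaving the text alone has real substance.

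- *The baricitinib clash is only apparent.* The third paragraph opens by speaking of other treatments, so it supplements the first. Prohibiting unlisted use does not authorize listed use against a specific ban. 6.5.1 and 6.5.4 confirm the strict rule. This stands: it is a drafting leftover. A reader might infer that guideline-listed off-study baricitinib is allowed; the documents do not support that.
- *Other JAK inhibitors are not unregulated.* A reader might infer that only baricitinib is prohibited at all on the JAK side. That is wrong, because the third paragraph prohibits the rest when no guideline lists them.
- *The asymmetry may be deliberate.* Exclusion 14 gives dose equivalents among glucocorticoids, so a class ban follows naturally there. No equivalence is given between JAK inhibitors, and the guideline rule also governs IL-6 antibodies, interferon and convalescent plasma. This explains the steroid wording. It does not explain why a drug of the same class as one randomized treatment is handled like an unrelated therapy, given the reason stated in the first paragraph.
- *Safeguards exist.* 7.1.1 lets the investigator stop study product when continued dosing is not in the patient's interest, 6.5.1 asks for plans to stop concomitant drugs for additive toxicity, 6.5.3 has prescriptions recorded to Day 29 or discharge, and the Endpoint Review Committee in 9.3 may review medications. These limit harm and leave a record. None of them prohibits the use.
- *The scenario may never occur.* The protocol shows no guideline listing another JAK inhibitor, and 2.1.1 says that only dexamethasone and baricitinib have shown efficacy in large randomized trials. This stands as a limit on size.

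**Conclusion.** The point holds as a gap in an operative rule. Before category 7, a second JAK inhibitor that a local or NIH guideline lists may be started for COVID-19 in either blinded arm, and 6.5.4 requires no deviation for it. The naming of baricitinib in the third paragraph of 6.5.2 is an inconsistency whose intended resolution is clear.

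The size is probably small and is not quantified. It depends on a guideline listing such a drug, on clinicians starting it before ventilation, and on its having an effect; the documents are silent on the first two and give no figure for the third. A reader might infer a material loss of power or a biased contrast. The protocol does not support that, and the power table rests wholly on assumed use and assumed benefit.

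That imatinib, gefitinib and acalabrutinib are called JAK inhibitors here and tyrosine kinase inhibitors in exclusion 12 is editorial and is not part of the point. The amendment is worth making because it is cheap and protects both the comparison and safety.

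**What to change.** 1. In the first paragraph of 6.5.2, and in the ban and deviation sentences of 6.5.4, replace baricitinib with *baricitinib and other JAK inhibitors given for COVID-19*.
2. Delete baricitinib from the examples in the third paragraph of 6.5.2.
3. Leave the existing steroid and held-oral-product exceptions unchanged.

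The words *given for COVID-19* keep a JAK inhibitor taken for a pre-existing condition under 6.5.1 and exclusion 17.

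The cost is one wording amendment, with no added patients, visits or procedures. The downside is that a site whose guideline lists another JAK inhibitor could not use it before ventilation, a restriction of the same kind as the one already placed on glucocorticoids.

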6.5.3 Assessment of Concomitant Therapies

Concomitant medications will be assessed from 7 days prior to enrollment to Day 29 or upon discharge, whichever comes first for all medications except corticosteroids. All corticosteroids (except nasal, ophthalmic, or topical steroids) including dexamethasone, prednisone, prednisolone,

Appendix D - ACTT-4: Baricitinib/Remdesivir vs Dexamethasone/Remdesivir and methylprednisolone should be recorded from Day -7 through Day 29 even after discharge from the hospital. Recording corticosteroid use after hospital discharge is important because long courses of po corticosteroids given after hospital discharge may impact our study endpoints. All prescription medications should be recorded during this time period with the exceptions listed in the bulletts below. All medications, except biologics and corticosteroids, can be recorded once regardless of the number of times it was given during the time period. For example, vasopressors should be recorded when first dose given (as the start date) and the last dose given (as the end date) during the period of assessment.

Sites do not need to record any of the following categories of medications in the eClinical system during the period from Day -7 through Day 29:

- All topical medications: ointments, creams, and lotions;
- All intranasal medications: nasal decongestants, nasal allergy medications, nasal steroids, and nasal saline drops/sprays;
- All ophthalmic medications: ophthalmic allergy medication, ophthalmic medications for infection, and ophthalmic medications for eye dryness (e.g., saline eye drops);
- Antiseptic mouth wash, lozenges;
- Cough medication: mucolytics, cough suppressants, and expectorates;
- GI medications: H2 blockers, proton pump inhibitors, GI stimulants, prokinetics, laxatives, stool softeners, antacids, anti-diarrheal and anti-nausea medications;
- Symptomatic care medications: antipyretics, antihistamines, decongestants, and NSAIDs;
- Mineral or herbal supplements, dietary supplements, iron/ferrous sulfate, magnesium, calcium, electrolyte replacement;
- Albumin infusions;
- Melatonin;
- Nicotine patch, lozenge, gum, or nasal spray, or other product to treat tobacco dependence;
- Dyes: contrast media, iodine – based dye, barium sulfate, and diatrizoate sodium.

See the MOP for more information about recording concomitant medications.

6.5.4 Progression to Intubation/Invasive Mechanical Ventilation.

In ACTT-4, non-study product (off-study) baricitinib, dexamethasone and other glucocorticoids are prohibited unless the subject worsens to require invasive mechanical ventilation (ordinal score 7). Mineralocorticoids for standard indications are permitted (e.g., adrenal insufficiency, shock). Low-dose prednisone as part of immunosuppression regimen for solid organ-transplant patients is allowed as part of standard of care (e.g., prednisone 5 mg po daily).

If additional (off-study) baricitinib, dexamethasone or another glucocorticoid is given when a subject is not an ordinal scale category 7, the investigator should file a protocol deviation for use of the prohibited medication and decide whether the blinded study products should be discontinued. The subject should remain on study and continue with the SOA as described in the protocol though the Day 60 visit. An exception to this is when oral study product is held for more than 2 days and the clinical condition requires that an open-label (off-study) dexamethasone or other anti-inflammatory agent be added while the oral study product is held (see Section 6.1.4).

- The preference is to continue study medication as originally assigned (i.e. continue blinded baricitinib or placebo and continue blinded dexamethasone or placebo) as well as the remdesivir infusions. The subject should remain on study though the Day 60 visit.
- Recognizing the treating clinician may request to stop the randomized blinded study medication, the next preferred option is that the baricitinib/placebo po component and the dexamethasone/placebo IV component are discontinued without unblinding. This will allow the treating clinician to pick any regimen needed for the subject. In this scenario, remdesivir infusions should continue and the subject should remain on study though the Day 60 visit.
- If the treating clinician needs to know prior treatment, the site investigator can request that the subject treatment assignment be unblinded. This is the least preferred option as it unblinds treatment assignment. However, it is available to ensure clinicians have information available to give their patients optimal care. In this scenario, remdesivir infusions should continue and the subject should remain on study through the Day 60 visit.

The above treatment choices will be tracked for all subjects that worsen to require mechanical ventilation (ordinal 7) and will be tracked by the sponsor. Sites that consistently unblind subjects in this category may have enrollment curtailed by the sponsor. The MOP Part A Clinical, Section 5 and an informational sheet for staff training located on the Emmes website titled, *Unblinding for Progression to Mechanical Ventilation*, describe the unblinding procedure and the documentation that is needed. It is important that sites know the procedure so that site staff, the site PI and other ACTT investigators, and the Sponsor remain blinded. The unblinded study pharmacist should only unblind the treating clinician to the treatment assignment if unblinding is deemed necessary.

